4.1 Preface

Rabies has the highest case fatality rate of any known human infectious disease and kills around 59,000 people annually. The vast majority (99%) of these fatalities occur in Africa and Asia due to canine rabies. While human rabies can be prevented with post-exposure prophylaxis (PEP), the intervention is expensive and often not available in the remote communities where it is most needed. Targeting control efforts at the reservoir host through mass dog vaccination (MDV) is a socially equitable and effective approach to eliminating human rabies. However, implementing MDV across the rural landscapes where rabies remains endemic is logistically challenging and, consequently, expensive. Moreover, there has only been limited empirical evidence to demonstrate the cost-effectiveness of MDV in achieving public health outcomes. As a result many countries spend substantial resources on provision of PEP with only limited investment in MDV and, without eliminating the transmission source, human rabies deaths continue. The standard method of delivering MDV across Africa is a centralized team-led strategy. Based in central locations where power supplies allow vaccine storage in cold-chain conditions (4°C), teams drive to rural villages and set up temporary MDV clinics. To eliminate rabies on a regional scale, these pulsed once-per-year campaigns must vaccinate at least 70% of each community's dog population in order to maintain the minimum coverage above 20-45% (critical threshold - Pcrit) throughout the year. Otherwise natural turnover in the dog population leads to drops in coverage that allow sustained rabies transmission. Achieving this coverage level consistently across remote landscapes with pulsed team-led delivery, which is expensive and often results in a heterogeneous coverage, is challenging. Novel, cost–effective MDV delivery strategies that enable consistently high vaccination coverage to be achieved at the scale required for regional elimination are urgently needed. Decentralized community-led delivery strategies are a promising way of improving access to health interventions and have been used in Africa for the control of neglected tropical diseases such as onchocerciasis. In the case of rabies control, it has been hypothesized that moving towards continuous vaccination throughout the year via a community-led model will improve consistency of coverage and reduce delivery costs relative to annual pulsed MDV. A key barrier to implementation of community-led interventions has been the inability to store rabies vaccines under cold-chain conditions in resource-limited rural communities. However, the availability of a thermotolerant rabies vaccine, storable without loss of potency for extended periods at temperatures exceeding cold-chain conditions, would allow community-led delivery options to be explored. Our recent study investigating immunogenicity of a widely used canine vaccine (Nobivac[™] Rabies) shows that immunogenicity to a protective level is not diminished following storage at 30°C for 3 months. This important outcome now enables implementation and testing of novel decentralized delivery strategies.

4.2 Purpose of the analyses

These analyses will assess the efficacy of community-led *continuous* MDV in comparison with standard team-led *pulsed* MDV.

5 Study Aims and Endpoints

5.1 Study Aims

Aim 1: Test the effectiveness of a decentralized community-led continuous delivery strategy against the standard centralized team-led pulsed delivery via a randomized controlled trial (RCT). We will carry out a RCT to compare metrics of vaccination coverage under these two intervention strategies. We hypothesize that community-led continuous MDV delivery will result in:

- higher mean coverage across each year;
- higher coverage at 11 months (because puppies should be vaccinated earlier in their lives than under pulsed MDV);
- lower likelihood (proportion of year) with coverage below the critical threshold of 40%;
- more consistent coverage over time;

• more consistent coverage over space (between villages).

Aim 2: Compare the cost-effectiveness of the two delivery strategies.

We hypothesize that a community-led continuous mass dog rabies vaccination strategy will enable higher levels of vaccination coverage to be achieved when compared to a team-led pulsed mass dog rabies vaccination strategy and at lower cost. The data generated will allow estimation and comparison of vaccination costeffectiveness and the net benefits of public health outcomes under the two MDV delivery strategies.

Aim 3: Assess the impact of the introduction of MDV across the Mara region on human health

We hypothesize that the introduction of MDV over a 3-year period to a region with little prior exposure to MDV will result in a reduction in numbers of dog bites and cases of human rabies. Note that the resolution of human health data does not allow these outcome measures to be compared between trial arms. This aim does not therefore assess the efficacy of the continuous MDV intervention.

5.2 Outcome measures

Primary efficacy outcome measure

Mean vaccination coverage across each year of the trial, which is equivalent to predicted coverage at 6 months. Coverage is defined as the proportion of dogs in each community (village) that have been vaccinated. A dog will be identified as having been vaccinated based on the possession by the owner of a vaccination certificate.

Secondary efficacy outcome measures

- 1. Vaccination coverage at 11 months.
- 2. Proportion of a year when coverage is predicted to be below the critical threshold of 40%.

- 3. Variability in coverage over time.
- 4. Variability in coverage between villages.

Cost-effectiveness outcome measures

Cost-effectiveness outcomes will be added in a future version of the SAP.

[figure not shown]
Human health outcome measures

- 1. Dog bite injuries assessed using hospital record data collected at district hospitals in the Mara region of Tanzania from October 2019 to August 2023.
- 2. Number of human rabies cases assessed using hospital record data collected at district hospitals in the Mara region of Tanzania from October 2019 to August 2023.

6 Study Methods

6.1 General Study Design and Plan

The study design will be a cluster randomised controlled trial in which the villages within 112 administrative wards will be randomly assigned to receive MDV through either of the two delivery strategies. The ward is the cluster. Randomisation will be stratified All district. wards will by be randomised before the start of the trial. Due to the nature of the intervention. the allocation of wards to treatment

arms will be unblinded to the participants (the ward population) and the research

team. However, the trial statistician will be blinded to the allocations until after the trial has been completed and the SAP has been approved.

6.2 Inclusion-Exclusion Criteria and General Study Population

The trial will take place in nine local government authority districts within the Mara Region of northern Tanzania. Each district is comprised of administrative wards, with each ward comprising three to four villages. The RCT will cover 112 wards and 428 villages in total. All wards within this study area will be included in the trial, therefore there are no inclusion or exclusion criteria at the cluster level beyond inclusion in the study area.

6.3 Randomisation and Blinding

Fifty-six wards will be randomly allocated to each of pulsed or continuous MDV (n=112) by permuted block randomisation with a block size of six wards, stratified by district. Randomisation will be carried out by running a program (a script for the R statistical software), written by the trial statistician, that will generate a spreadsheet assigning each ward to a treatment arm. To maintain blinding of the trial statistician to the treatment allocations, a statistician with no connection to the study ([name], University of Glasgow) will run the program using a different random seed chosen by and known only to him. He will send the spreadsheet of treatment allocations directly to the Chief Investigator. An additional 19 wards (n=131) might be included in the trial if time and costs allow. In order to preserve the integrity of the randomisation, the spreadsheet will include a randomisation order within each district indicating the order in which wards should be enrolled in the study.

6.4 Study Variables

	Baseline	Year 1–3	Year 1-3	Year 1-3
		Month 2	Month 11	Monthly
Coverage in pulsed arm		Х	X	
Coverage in continuous arm		Х	X	
Human dog bite injuries	Х			Х
Human rabies cases	Х			Х
Dog rabies cases	Х			Х
Cost/dog of delivery (pulsed)				Х
Cost/dog of delivery (continuous)				Х

7 Sample Size

We estimate that randomizing 56 wards to each arm of the trial will give 87% power at the 5% significance level to detect coverage superiority of continuous to pulsed MDV delivery, assuming a mean coverage (the mean of coverage at 2 and 11 months) of 50% with pulsed and 58% with continuous delivery (equivalent to an odds ratio of 1.34). Power was estimated by analysing 10,000 simulated data sets, assuming sampling of one village per ward, three sub-villages per village, 10 households per sub-village and an average of 2.5 dogs per dog-owning household (a total of 9,000

dogs per assessment) at 2 and 11 months for three years. Logit-normal variances between households (11.5), sub-villages (4.4), villages (0.55) and wards (0.023) and the distribution of dogs over households were based on survey data from previous studies, and have an effect on required sample size equivalent to a design effect of 23. On the basis of following up vaccinated dogs in 112 study villages corresponding to 112 wards, we expect to record coverage in approximately 43,700 dogs in the first phase of the trial and a further 16,100 in each of the second and third years (assuming half of the dogs selected for follow-up each year will have died and been replaced with new dogs by the next). Mean coverage at 2 months in both arms was assumed to be 60% following static-point vaccination clinics. Mean coverage is an exponentially distributed lifespan with a mean of 26 months), while declining less sharply to 55% in Arm 2 due to ongoing vaccination of puppies. If time and costs allow, the more villages in addition to the central village could be included.

8 General Considerations

8.1 Timing of Analyses

The final statistical analysis will be performed after the study has closed and all of the outcome data has been delivered to the trial statistician. To maintain blinding of the trial statistician, these data will not include the allocations of the wards to the study arms. The final primary analysis will be developed and approved using dummy allocations, before the final analysis is performed using the true allocations.

8.2 Analysis Populations

It is not expected that any wards will drop out during the trial, therefore the analysis population will be the full population of 112 wards, which is the intention to treat (ITT) population.

8.3 Covariates and Subgroups

The final analysis model will allow include random effects to allow for clustering of the outcome measures at the level of districts and wards, sub-villages and households. Where possible, two types of random effect will be fitted at each level, allowing clustering that is both consistent over the six survey visits, and specific to each survey visit. The efficacy analyses will not be adjusted for any ward characteristics. Subgroup analyses will be performed by tribal group and by prior exposure to MDV.

8.4 Missing Data

Missing data on a large scale (e.g. loss-to-follow-up of entire wards) is not expected. Missing data on a small scale (e.g. the trial team cannot collect outcome data at a particular time point in a particular village) is possible. Sparsely missing outcome data is effectively naturally imputed in random effects models.

9 Summary of Study Data

All continuous variables will be summarised using the following descriptive statistics: n (non-missing sample size), mean and standard deviation. Categorical variables will be summarised with frequency and percentages (based on the non-missing sample size) of observed levels. All summary tables will be structured with a column for each treatment in the order (pulsed, continiuous) and will be annotated with the total population size relevant to that table/treatment, including any missing observations.

10 Efficacy Analyses

Primary efficacy analysis

Mean vaccination coverage will be compared between the two arms using a generalized linear mixed-effects regression model (GLMM) fitted using maximum likelihood. Logit-normal random effects will be fitted to account for variation in coverage between districts, wards, subvillages and households. For each of these levels, except household, additional round-specific random effects will be included to allow for unexplained variation in coverage that is inconsistent between rounds. Intervention arm, assessment visit (2 or 11 months) and year will be modelled as fixed effects. All three two-way interactions and a three-way interaction between year, visit, and arm will be fitted. The effect of fitting these interactions will be to allow coverage to differ between the six rounds (year \times visit), and to allow the intervention effect to differ between the six rounds (arm imes year, arm imes visit, arm imesyear \times visit). The primary analysis will be a test of the null hypothesis of equal coverage (Arm One (pulsed) : Arm Two (continuous) odds ratio = 1) between continuous and pulsed delivery against the two-sided alternative hypothesis of unequal coverage. The full model, including the main effect of trial arm and the arm \times year, arm \times visit, and arm \times year \times visit interactions, will be compared with a null model not including trial arm or its interactions with round or year. In effect, the null model allows coverage to vary over the six time points (the six household surveys), while the full model includes an additional six parameters that allow coverage to vary independently between trial arms at each of the six time points. Under the null hypothesis, therefore, there is no intervention effect at any of the six time points, while the alternative hypothesis is that there is an intervention effect at one or more time points.

The intervention effect will be estimated as an odds ratio with 95% confidence interval and the null hypothesis will be tested using a likelihood ratio test and rejected at the 5% significance level if p < 0.05. If the null hypothesis is rejected and the continuous:pulsed odds ratio > 1 then community-led delivery will be considered superior.

Secondary efficacy analyses

- 1. Vaccination coverage at the eleven-month time point within each annual vaccination cycle will be compared between arms in order to test the hypothesis that eleven-month vaccination coverage in the community-led delivery arm is higher than the coverage at the same time-point in the team-led delivery arm. A model including the fixed effects of year, trial arm, and their interaction will be compared with a model with only year as a fixed effect. Both models will be fitted to data from the second (11-month) visit only, excluding data from the first (2-month) visit.
- 2. The full model will be used to compare the likelihood of coverage dipping below the threshold of 40% in each arm by implementing the following plan:
 - a. Use parametric bootstrapping from the fitted full model to generate at least 1000 samples from the sampling distribution of the model parameters, capturing uncertainty in the model parameter estimates (fixed effects and random effect variances).
 - b. For each of the 1000 sets of parameters, simulate a new set of wards with ward-level coverage, including random effect variation, giving the distribution of predicted coverage in each arm for a random ward, taking account of parameter estimation uncertainty and random effect variation.
 - c. Calculate the proportion of wards with coverage below 40% for each arm, using the 1000 parametric bootstrap samples to calculate 95% confidence intervals.
- 3. The hypothesis that variation in vaccination coverage over the three-year time frame of the study was lower in the community-led arm than in the team-led arm will be tested. The fixed effects of assessment visit and year will be replaced by a variance parameter to capture variation in coverage over time. A model representing the null hypothesis, with the temporal variance constrained to be equal between continuous and pulsed delivery, will be compared to a model where these variances are allowed to differ. These models may be fitted using Markov Chain Monte Carlo (MCMC) because variance component estimation can be more reliable than using maximum likelihood. The null hypothesis of equal variances will be rejected if the 95% CI for the ratio of variances (continuous:pulsed) does not include 1, and

continuous delivery will be considered more consistent than pulsed if the upper bound of the 95% CI is below 1.

4. Using the same methods (except that the target of inference will be the continuous:pulsed ratio in inter-village variance) the null hypothesis of equal inter-village variation in vaccination coverage will be tested.

Cost-effectiveness analyses

Cost-effectiveness analyses will be added in a subsequent version of the SAP.

Human health outcome analyses

Human health outcome analyses will be added in a subsequent version of the SAP.

11 Figures

Analyses comparing efficacy outcomes (coverage and consistency) between the study arms will be illustrated by figures showing for each arm the mean outcome with 95% confidence limits over the three years of the trial.

12 Reporting Conventions

P-values ≥0.001 will be reported to 3 decimal places; p-values less than 0.001 will be reported as "<0.001". The mean, standard deviation, and any other statistics other than quantiles, will be reported to one decimal place greater than the original data. Quantiles, such as median, or minimum and maximum will use the same number of decimal places as the original data. Estimated parameters, not on the same scale as raw observations (e.g. regression coefficients) will be reported to 3 significant figures.

13 Technical Details

All analyses will be performed in the most recent version of the R statistical software and its packages. Maximum likelihood GLMMs will be fitted using the Ime4 package. Bayesian models will be fitted using MCMC in the runjags and/or MCMCgImm packages. Quality measures will include comparison of source and analysis data sets and code-review.

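### Secondary 2 compares the arms' shares of wards below 40% coverage using a model that gives both arms the same between-ward spread, although Aim 1 and secondary 4 expect that spread to differ

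*SAP*

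**What the plan says.** Section 10, secondary analysis 2, names its model: "The full model will be used to compare the likelihood of coverage dipping below the threshold of 40% in each arm". It takes parametric bootstrap samples of that model's parameters, and for each sample it will "simulate a new set of wards with ward-level coverage, including random effect variation". The final step is: "Calculate the proportion of wards with coverage below 40% for each arm". It does not say at which survey round coverage is evaluated.

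The full model is defined under the primary analysis: "Logit-normal random effects will be fitted to account for variation in coverage between districts, wards, subvillages and households". At every level except household, "additional round-specific random effects will be included to allow for unexplained variation in coverage that is inconsistent between rounds". Arm appears only in the fixed part: compared with the null model, "the full model includes an additional six parameters that allow coverage to vary independently between trial arms at each of the six time points".

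Variances that may differ by arm appear only in secondaries 3 and 4. In secondary 4, "the null hypothesis of equal inter-village variation in vaccination coverage will be tested", with the continuous:pulsed ratio of inter-village variance as the target. Aim 1 (section 5.1) gives the expected direction, which is more even coverage between villages under continuous delivery. The Preface (section 4.1) says that coverage from team-led pulsed delivery is often heterogeneous.

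**The concern.** The share of wards below a threshold is a tail probability. It depends on the arm's mean and on the spread of wards around that mean. Secondary 2 lets the mean differ by arm but holds the spread equal.

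The spread in question is the one that the trial expects to differ. The sample size section assumes one village per ward, and the analysis model has no village term, so the ward term carries the between-village variance.

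The report could therefore find unequal variances under secondary 4 and, beside it, give threshold risks under secondary 2 that assume them equal. Bootstrapping does not repair this, because it carries the uncertainty of one shared variance and never a difference between arms. If better consistency is part of how continuous delivery works, secondary 2 as written cannot credit that part.

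**Working it through.** **Inputs from the SAP (section 7).** Logit-scale variances are household 11.5, sub-village 4.4, village 0.55 and ward 0.023. With one village per ward, the ward-term variance is 0.55 + 0.023 = 0.573, and the variance within wards is 11.5 + 4.4 = 15.9. Mean coverage is 50% pulsed and 58% continuous. Coverage at month 2 is 60% in both arms, and continuous coverage at month 11 is 55%. The sentence giving pulsed coverage at month 11 is damaged in the text. A mean of 50% with 60% at month 2 implies 2 × 50 − 60 = 40%. Exponential loss with a 26-month mean lifespan over nine months gives 60% × exp(−9/26) = 42.4%. Both values are used.

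**Assumed.** The SAP gives no variance ratio, so continuous:pulsed ratios of 0.75, 0.5 and 0.25 are tried, with the average held at 0.573: pulsed variance = 2 × 0.573/(1 + ratio). A ratio of 0.5 gives 0.764 and 0.382. District and round-specific variances are not given and are left out.

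**The plan's own figure.** The figure built on these variances is the 87% power. A simulation of 56 wards per arm, with ward, village and sub-village effects kept over rounds and households redrawn, gave 88.2% for a constant 50% v 58% and 85.2% for 60%/40% v 60%/55%. Ward means were compared by t-test as a stand-in for the GLMM. Keeping households as well gave 83.3% and 79.5%. The variances are thus consistent with the stated power under the first reading. This point disputes no figure in the SAP.

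**Formula.** Ward coverage is the inverse logit averaged over sub-village and household effects.
- Threshold t: the mean of expit(t + N(0, 15.9)) equals 0.40, which gives t = −1.106.
- Arm intercept b: the mean of expit(b + N(0, 15.9 + v)) equals the arm's mean coverage.
- Share of wards below 40% = Φ((t − b)/√v).

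**At the plan's mean coverage, ratio 0.5.**
- Common variance, pulsed (b = 0): Φ(−1.106/√0.573) = Φ(−1.46) = 7.2%.
- Common variance, continuous (b = 0.894): Φ(−2.000/√0.573) = Φ(−2.64) = 0.4%. The difference is 6.8 points.
- True variance, pulsed: Φ(−1.106/√0.764) = Φ(−1.27) = 10.3%.
- True variance, continuous (b = 0.890): Φ(−1.996/√0.382) = Φ(−3.23) = 0.1%. The difference is 10.2 points.

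**Other settings** (pulsed/continuous, then difference in points):

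| Mean coverage | Ratio | Common variance | Arm-specific variances |
|---|---|---|---|
| 50% v 58% | 0.75 | 7.2%/0.4%, 6.8 | 8.6%/0.2%, 8.4 |
| 50% v 58% | 0.25 | 7.2%/0.4%, 6.8 | 12.4%/0.0%, 12.4 |
| Month 11, 42.4% v 55% | 0.5 | 36.5%/1.4%, 35.1 | 38.4%/0.4%, 38.1 |
| Month 11, 40% v 55% | 0.5 | 50.9%/1.4%, 49.5 | 51.0%/0.4%, 50.7 |
| 35% v 55% | 0.5 | difference 77.3 | difference 75.4 |
| Month 2, 60% v 60% | 0.5 | difference 0 | difference 0.5 |

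**Sensitivity to how a ward is simulated.** If ward coverage is averaged over only three simulated sub-villages, ratio 0.5 at 50% v 58% gives 23.7%/7.6% true and about 22.8%/8.4% under the common variance. The differences are 16.1 and 14.4 points, so the gap falls from 3.4 to 1.7.

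**Precision of an arm-specific variance.** A balanced ANOVA approximation uses n = 56 wards, k = 3 sub-villages and s = 4.4, treats sub-village effects as known, and assumes the same sub-villages are resurveyed. With M = kv + s, SE = √[2M²/(n − 1) + 2s²/(n(k − 1))]/k. At v = 0.573, M = 6.119 and SE = √(1.362 + 0.346)/3 = 0.44. The estimate falls at or below zero in about 17% of trials at v = 0.38 and 26% at v = 0.25. Pooling both arms at 0.573 gives an SE of 0.31 and about 3%.

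**The case against.** The SAP never says in so many words that the variances are common. That is inferred, but securely: a full model that adds exactly six arm parameters, one per round, leaves no room for arm-specific variances, and the SAP names such variances where it wants them.

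The stronger objections concern size and direction, and they largely stand.
- A reader might put both arms at 50% and conclude that the method reports 7.2% in each arm when the truth is 12.2% v 1.4% (variances 0.90 and 0.25). The arithmetic is right, but the plan assumes 50% v 58%, and no document gives that variance split.
- A reader might infer that the bias always runs toward no difference. It does not. If pulsed coverage is below 40%, a larger variance lowers the share of wards below the threshold. At 35% v 55% the common-variance model slightly overstates the difference.
- A dip below 40% is most likely at month 11. There the plan's own assumptions put pulsed coverage close to 40%, where the distortion is small against a large difference.
- Step (b) does not say how ward coverage is built from sub-villages, and one plausible choice roughly halves the gap.

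Pooling is also a defensible trade of bias for precision, given how poorly an arm-specific ward variance is estimated. This argues against replacing the common-variance analysis. It does not argue against showing the other result, because realised means and variances are unknown in advance and the trial's own hypothesis is that the variances differ.

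**Conclusion.** The inconsistency is real. Secondary 2 imposes equal between-ward spread on a quantity that depends on that spread, while Aim 1 and secondary 4 expect and test a difference in it. Under a variance ratio of 0.5, the difference in shares is 6.8 points as planned against 10.2 in truth at mean coverage of 50% v 58%. Over ratios from 0.75 to 0.25 the true value runs from 8.4 to 12.4. At month 11 the planned analysis gives about 35 to 49 points against 38 to 51, which would not change a conclusion.

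These sizes rest on assumed variance ratios, on a ward variance of 0.573, on one village per ward, and on averaging fully over sub-villages. If the variances are in fact equal there is no bias. The point does not touch the primary analysis, and the documents do not support a claim that secondary 2 would in general miss or reverse a benefit.

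**What to change.** In section 10, secondary 2, add that the shares below 40% will also be computed, by round, from a model with arm-specific ward and ward-by-round variances, and reported beside the common-variance result. State that a lack of difference under the common-variance model will not be read as equal risk if the two results disagree. State also how many sub-villages are simulated per ward, or that they are averaged out.

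The MCMC route that the SAP already allows for secondary 4 is preferable, because lme4 estimates of an arm-specific ward variance may fall at zero and make the tail share degenerate. The model used must keep fixed effects for arm at each round. Secondary 3 replaces visit and year by a variance term, and secondary 4 borrows its methods, so this needs saying. If the optional extra villages are surveyed, the arm-specific variance should sit on a village term.

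The cost is SAP wording, one extra model fit and noticeably wider intervals for the added result, since the arm-specific ward variance is imprecise with 56 wards of three sub-villages each.

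### Secondary outcome 2 is defined as a share of the year with coverage below 40%, but its analysis calculates a share of wards, at no stated round and with no between-arm contrast specified

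*SAP*

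**What the plan says.** Section 5.1 lists among the hypotheses for continuous delivery a "lower likelihood (proportion of year) with coverage below the critical threshold of 40" per cent, so the word likelihood is explained there as a share of the year. Section 5.2 repeats this as secondary outcome 2: "Proportion of a year when coverage is predicted to be below the critical threshold of 40" per cent.

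Section 10, secondary efficacy analyses, item 2 opens: "The full model will be used to compare the likelihood of coverage dipping below the threshold of 40% in each arm". Three steps follow. Step a draws at least 1000 parameter sets by parametric bootstrap. Step b simulates new wards, "giving the distribution of predicted coverage in each arm for a random ward". Step c reads: "Calculate the proportion of wards with coverage below 40% for each arm, using the 1000 parametric bootstrap samples to calculate 95% confidence intervals".

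The full model behind these steps is that of the primary analysis: "Intervention arm, assessment visit (2 or 11 months) and year will be modelled as fixed effects". With three years and all interactions, it gives a separate mean for each arm at each of six surveys.

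**The concern.** A share of time and a share of wards are different estimands. The first needs a path of coverage through the year for each unit. The second needs a moment at which every unit is judged. Steps a to c supply neither: there is no rule for coverage between the two visits, and it is not said whether a ward is judged at month 2, at month 11, in a particular year, or over all six surveys pooled. The steps also stop at one proportion and interval per arm, although Section 5.1 states a directional hypothesis between arms.

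At stake is whether a declared efficacy outcome can be reported at all, and whether the number reported under its name was fixed in advance. Section 8.1 provides for development and approval under dummy allocations, but names only the primary analysis. The round, the curve and the contrast for this outcome therefore need to be fixed in the SAP text.

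**Working it through.** **Comparison of the text**

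| Element | Sections 5.1 and 5.2 | Section 10, item 2 |
|---|---|---|
| Quantity | Share of a year below 40% | Share of wards below 40% |
| Time | The whole year | Not stated; the model has six time points |
| Path between visits | Needed | Not given |
| Arms | Directional hypothesis | Intention to compare; per-arm intervals only |

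In the same section, item 1 names the 11-month visit and a comparison of models with and without arm. Items 3 and 4 name a continuous:pulsed ratio with a rule based on its interval. Item 2 has no counterpart to these.

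**How far apart the quantities are**

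The SAP gives no figure for this outcome, so there is none to reproduce. What follows is an illustration.

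Inputs from Section 7:
- Month 2 coverage is 60% in both arms; month 11 coverage is 55% in the continuous arm.
- Pulsed month 11 has two readings. The 26-month mean exponential lifespan gives 0.60 × exp(−9/26) = 42.4%. The stated pulsed mean of 50% over months 2 and 11 gives 2 × 50% − 60% = 40%. The sentence on the decline is broken in the extracted text, so both are carried.
- Logit variances are household 11.5, sub-village 4.4, village 0.55 and ward 0.023, total 16.473.

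Assumptions of this check:
- Village and ward variance are pooled (0.55 + 0.023 = 0.573, SD 0.757), because one village is sampled per ward. The remaining 15.9 is averaged over to obtain ward coverage.
- Round-specific variances are not given and are left out.

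Formulae, with Z standard normal:
- η(p) solves E[expit(η + √16.473 Z)] = p. This gives η = 1.122 at 60%, 0.557 at 55%, −0.844 at 42.4% and −1.122 at 40%.
- The ward-level threshold τ solves E[expit(τ + √15.9 Z)] = 0.40, so τ = −1.106.
- Share of wards below 40% = Φ((τ − η)/0.757).

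Share of wards below 40%:
- Both arms, month 2: Φ(−2.94) = 0.2%.
- Pulsed, month 11: Φ(−0.35) = 36.5% (mean 42.4%), or Φ(0.02) = 50.9% (mean 40%).
- Continuous, month 11: Φ(−2.20) = 1.4%.
- Pulsed, both visits pooled: (0.2 + 36.5)/2 ≈ 18%, or (0.2 + 50.9)/2 ≈ 26%.

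Share of ward-time below 40%, averaging the share of wards over the period. The path through months 2 and 11 is assumed to be linear, exponential or linear on the logit scale:
- Pulsed, months 0–12: 10.7% to 11.4% (month 11 at 42.4%), or 15.1% to 16.3% (40%).
- Pulsed, months 2–11 only: 9.6% to 10.6%, or 13.8% to 15.4%.
- Continuous: 0.6% over either period.

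The between-arm difference (continuous minus pulsed) is thus zero at month 2. At month 11 it is 1.4 − 36.5 = −35.1 to 1.4 − 50.9 = −49.5 percentage points. As a share of months 0–12 it is 0.6 − 10.7 = −10.1 to 0.6 − 16.3 = −15.7 points.

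**Sensitivity to the variance used**

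With ward variance 0.023 alone (SD 0.152, τ = −1.122), the pulsed share of wards at month 11 is 3.4% (mean 42.4%) or 50% (mean 40%). The share of months 0–12 is about 1% or 9%. The figures move a great deal, but the dependence on the unstated time remains.

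**The case against.** **Item 2 does say that the arms will be compared.** Both arms come from one joint model and the same bootstrap draws, so a difference with an interval is readily formed. This stands. A reader might infer that the arms are never compared; the lead sentence of item 2 does not support that. What is missing is the contrast, its interval and a decision rule.

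**A path through the year is implied.** Section 5.2 equates the yearly mean with predicted coverage at 6 months, so some interpolation must be in mind. But no curve is stated there or in item 2, and step c counts wards, not time.

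**The unit is not a real problem.** Section 5.2 says "Coverage is defined as the proportion of dogs in each community (village) that have been vaccinated", whereas step c counts wards, and a reader might infer a serious change of unit. Section 7 plans one village per ward and the Section 10 model has no separate village level, so the ward effect absorbs village variation. The difference would matter only if the optional extra villages were added.

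**The size rests on assumptions.** This also stands. Month 11 in the pulsed arm has two readings, and the path through the year is not the SAP's. On the 42.4% reading the pulsed mean does not reach 40% until 2 + 26 × ln(1.5) = 12.5 months, so a reader might add 0% as a possible result. Step b includes random-effect variation, so the plan would not report the time that the arm mean alone spends below 40%.

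**Late-cycle coverage is tested elsewhere.** Item 1 compares the arms at 11 months. That limits the harm, but it concerns mean coverage and not time below a threshold.

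**Conclusion.** The point holds. The definition and the analysis of secondary outcome 2 describe different quantities, the analysis names no time, and the intended comparison between arms has no specified contrast. This is a contradiction within the SAP, not detail that could be left to a protocol.

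The mismatch follows from the text alone. Its size is illustrative: with pooled variance, the pulsed result could be about 0.2%, 18% to 26%, or 36.5% to 51% of wards according to the round chosen, against 11% to 16% of the year. These figures depend on the planning coverages and variances, the pooling of village and ward, the omission of round-specific variance and the assumed path.

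A reader might infer that the trial's main conclusion is at risk. The SAP does not support that: the primary test, the sample size and the superiority rule do not use this outcome. It should be fixed, as one of four secondary outcomes.

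**What to change.** Amend Section 5.2 and Section 10, item 2 together, before allocations are revealed, by one of two routes.

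(a) Keep a share of time. In each bootstrap draw, simulate ward coverage at months 2 and 11 of each year, averaging over household and sub-village effects. Interpolate on one prespecified curve over months 2–11, for example linear on the logit scale, and calculate the fraction of that period below 40%. Average within arm. Repeat with a second named curve, for example exponential, as a sensitivity analysis. State in Section 5.2 that the period is months 2–11.

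(b) Redefine the outcome in Sections 5.1 and 5.2 as the proportion of wards below 40% at the month-11 visit, and state in step c whether years are averaged or shown separately.

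Under either route, take continuous minus pulsed within each draw, report it with a bootstrap 95% interval, and conclude in favour of continuous delivery if the upper bound is below 0.

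The cost is SAP wording and a few lines of code on a bootstrap already planned. The downside of (a) is an interpolation assumption that two visits a year cannot verify. In the illustration, the choice of curve moves the pulsed result only from 9.6% to 10.6%, or from 13.8% to 15.4%. The downside of (b) is that the outcome is no longer a share of time.
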